## Tool Revision History

Version Number 1.1

Version Date 10/30/13

Summary of Revisions Made:

- 1) Clarified determination of adverse event severity with reference to neonatal toxicity tables (Appendix D) and additional guideline for assessing laboratory values (Appendix E) (see section 7.4.1).

Version Number 2.0

Version Date 6/30/2018

Summary of Revisions Made:

- 1) Changes in IND personnel. [name] will assume responsibilities as the sponsor-investigator (see letters from Drs. [name] and [name]). New study personnel have been added.
- 2) Changed the number and timing of visits. Since the differentiation between preterm infants with normal intestinal barrier maturation and those with delayed maturation was significant at the second timepoint (Study d8) or approximately 7-10 days of age, we will limit the dual sugar solution administration to one administration per subject between d7 and 10 of postnatal age.
- 3) Eliminate blood draws for zonulin measurement. There was no association of serum zonulin and the gold standard urinary Lactulose/Rhamnose ratio in the initial cohort of 43 subjects, so no further blood draws will be done.
- 4) Safety Monitoring: The U. Maryland IRB has approved the change from a DSMB to a single safety monitor.
- 5) Stool microbiome: Addition of stool microbiome analysis in relation to intestinal permeability measured by La/Rh ratio.

Version Number 2.1

Version Date 8/6/2019

Summary of Revisions Made:

- 1) Increase the sample size: Sample size will be increased to total 200 based on sample size calculation. A total of 200 sample size was calculated to obtain high precision in correlations between features of the stool microbiota and intestinal permeability (IP). Since 83% subjects in the first cohort had high IP ( $La/Rh \geq 0.05$ ) at study day 8, a sample size of 166-236 provides marginal error of 0.05 (maximum sampling error of 5%) and alpha of 0.05 (95% confidence level) to detect correlations between features of the microbiota and changes in IP and to achieve an expected sensitivity of 0.8-0.9 and expected specificity at 0.9-0.95.

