### 2.3 Preliminary Data

[figure not shown]

**Figure 1.** Microbial community diversity and intestinal permeability at study time points day 1, 8, and 15 for a cohort of 43 preterm infants (<33 weeks gestational age). Microbial community diversity is calculated as OTU richness based on 16S rRNA gene amplicon high-throughput sequencing. Intestinal permeability was calculated as the ratio of non-metabolized sugar probes

gestational age (<31.7wk) were identified to be the most discriminatory features for elevated IP by supervised learning scheme, reaching an accuracy of 86.1%. (5) *Clostridiales* and *Bifidobacteriales* are the most abundant bacteria groups in later stages (phase II/III at 6-18

Our analysis of the initial cohort of 43 preterm infants recruited for the IND protocol, and others' previous studies have shown that IP is high at birth in preterms (<33wk gestation) with a rapid maturation of the intestinal barrier over the first 2 weeks. However, in some infants, high IP persisted and/or recurred in association with altered levels of the normal microbiota (bacteria community composition). Specifically, we observed that (1) rapid maturation of intestinal barrier function, characterized by decreased IP, correlates with increased microbial community diversity (Figure 1), and most outstandingly, the increased abundance of beneficial bacteria *Clostridiales* (Figure 2); (2) *Clostridiales* is highly transcriptionally active and co-active with the probiotic bacterium *Bifidobacterium*; (3) neonatal factors, including early introduction of breast milk, shorter period of antibiotic exposure, and later gestational age, favor the early colonization of the gut microbiota by members of *Clostridiales* and *Bifidobacterium*, which altogether are associated with improved intestinal barrier in preterm infants; (4) low *Clostridiales* spp. abundance (<5%) and early

months of age) as shown in Figure 2, suggesting a process of gaining prosperity of these two bacterial groups during intestine development after birth. Altogether our preliminary results suggest the early colonization of the natural occurring probiotics strains *Clostridiales* and *Bifidobacterium* strongly associate with rapid maturation of intestinal barrier function, and their measurement are highly promising for early detection and as potential nutritional supplement to prevent NEC in the high-risk preterm population.

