We propose in this study to recruit additional 157 preterm subjects and to combine with our existing 43 preterm subjects to form a statistically powered cohort at 200 (justified in study size analysis in research design), to address our hypothesis that the two naturally occurring beneficial bacteria *Clostridiales* and *Bifidobacterium* are rapidly gaining prosperity during normal intestine development in association with improved barrier function measured by La/Rh ratio. Overall, this continuation of the initial study builds on the previous findings that identified commensal bacteria *Clostridiales* and *Bifidobacterium* species as a strong indicator to the lowered IP and rapid maturation of intestinal barrier, to substantiate measurement of these probiotic strains combined with associated neonatal factors to form an accurate, rapid detection of intestinal permeability abnormality.

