### **2.5 Study Objectives**

The proposed study will evaluate the intestinal permeability measured by the urinary La/Rh ratio at one timepoint between d7-10 of life in 200 preterm infants 24-32 weeks gestation in preparation for a future study of probiotics to improve intestinal permeability in this population.

**Primary Objective:** To estimate mean, variance, and quantiles in IP measured by urinary Lactulose/Rhamnose ratio at 7-10d of life in neonates born between 24 and 32 weeks of gestational age.

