### **4.5.2 Handling of Withdrawal**

Subjects who discontinue due to being withdrawn or lost to death will be replaced. Data and specimens will be de-identified and remain as part of the study.

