### **7.6 Halting Criteria/Rules**

#### **7.6.1 Stopping Rules for Individual Subjects**

A pre-dose checklist for evidence of feeding intolerance will be completed prior to La/Rh administration. The Lactulose/Rhamnose administration will be re-scheduled within the study window if the clinically indicated gastric residual is obtained and measures >50% of the previous nutritive feeding volume, and/or contains bile or gross blood, or is hemoccult-positive. If these GI signs are present throughout the study window, the La/Rh test will not be administered. Other conditions that would result in delay or discontinuation of the La/Rh test include hypotension requiring pharmacologic support, clinical or radiographic signs of intestinal ileus or NEC. The subject will continued to be followed until postnatal day 21±2 d or discharge/transfer which ever occurs first.

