## 10 STATISTICAL CONSIDERATIONS

### 10.5 Sample Size Considerations

Sample size for primary objective: The sample size for the first aim (50 subjects) will provide good precision in the estimate of the distribution of levels of intestinal permeability at each time point. The quantiles will be accurate +/- 10 percentage points (based on a 95% confidence interval). Based on the sites' combined annual admission numbers and survival rates, we expect 120 infants to be eligible in the 6 month planned enrollment period in the first year. The combined NICU population is approximately 59% male with an ethnic distribution of 65% African-American, 33% Caucasian and 2% other.

Sample size for microbiome analysis: The sample size of 200 was calculated to obtain high precision in correlations between features of the stool microbiota and intestinal permeability (IP). Since 83% subjects in the first cohort had high IP ( $La/Rh \geq 0.05$ ) at study day 8, a sample size of 166-236 provides marginal error of 0.05 (maximum sampling error of 5%) and alpha of 0.05 (95% confidence level) to detect correlations between features of the microbiota and changes in IP and to achieve an expected sensitivity of 0.8-0.9 and expected specificity at 0.9-0.95.

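### With 83% of infants high IP, 166-236 infants cannot give a 0.05 margin for specificity 0.90-0.95 (about 34 low-IP infants at N=200), nor for sensitivity 0.80

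*Combined protocol and SAP*

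**What the plan says.** The microbiome paragraph of section 10.5 starts from 83% of the first cohort being high IP at study day 8. It then states that "a sample size of 166-236 provides marginal error of 0.05 (maximum sampling error of 5%) and alpha of 0.05 (95% confidence level") for correlations between microbiota features and change in IP, and "to achieve an expected sensitivity of 0.8-0.9 and expected specificity at 0.9-0.95". The chosen total is 200. No formula is given, and there is no separate count of low-IP infants or separate calculation for specificity.

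The same statement stands in the version 2.1 entry of the Tool Revision History, introduced by "Sample size will be increased to total 200 based on sample size calculation". Section 2.3 relies on it when it combines 157 new infants with the existing 43 "to form a statistically powered cohort at 200 (justified in study size analysis in research design"). The Final Analysis Plan (section 10.6) uses the binary IP class as the reference for sensitivity, specificity, predictive value and ROC curves of three stool markers, and for a high/low-IP classifier.

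**The concern.** Sensitivity is estimated in high-IP infants and specificity in low-IP infants. If 83% are high IP, the low-IP class is small, and a total that suits sensitivity will be far too small for specificity. One margin is nevertheless offered alongside both.

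This sentence is the only stated basis for enlarging the cohort to 200. A reader would take it that specificity will be known to within 5 points. Specificity is the measure with the least data behind it, and section 2.3 aims at an accurate, rapid way to detect abnormal permeability.

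**Working it through.** **Inputs, all from section 10.5.** High-IP share 0.83, so low-IP share 0.17; margin d = 0.05; 95% confidence, taken as two-sided (z = 1.96); sensitivity 0.80-0.90; specificity 0.90-0.95; N = 200, range 166-236.

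**Formula.** N = z² p(1−p) / (d² × class share), with share 0.83 for sensitivity and 0.17 for specificity.

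**Reproducing the printed range.**
- Sensitivity 0.90: 3.8416 × 0.09 / 0.0025 / 0.83 = 166.6
- Sensitivity 0.85: 3.8416 × 0.1275 / 0.0025 / 0.83 = 236.0

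These match 166 and 236. The range is therefore what a sensitivity-only calculation for 0.85-0.90 would give.

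**The stated values that the range does not cover.**
- Sensitivity 0.80: 3.8416 × 0.16 / 0.0025 / 0.83 = 296.2, about 297 infants
- Specificity 0.95: 3.8416 × 0.0475 / 0.0025 / 0.17 = 429, about 430 infants (73 low IP)
- Specificity 0.90: 3.8416 × 0.09 / 0.0025 / 0.17 = 813.5, about 814 infants (139 low IP)

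**Precision available within the range.** Low-IP infants number 0.17 × N. The half-width is 1.96 √(p(1−p)/n); the Wilson 95% interval is also shown.

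| N | Low IP | Specificity 0.90: half-width; Wilson | Specificity 0.95: half-width; Wilson |
|---|---|---|---|
| 166 | 28 | 0.111; 74-97% | 0.080; 80-99% |
| 200 | 34 | 0.101; 76-96% | 0.073; 82-99% |
| 236 | 40 | 0.093; 77-96% | 0.067; 84-99% |

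For sensitivity at N=200 (166 high IP), 0.80 has half-width 0.061 (Wilson 73-85%) and 0.90 has 0.046 (84-94%). Setting 1.96 √(p(1−p)/166) = 0.05 gives p = 0.877, so the margin is met only from about 0.88 upwards.

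**Uncertainty in the 83%.** No count out of 43 rounds to 83%, so 35/42 is assumed here. Its exact 95% interval is 69-93%, which means about 14 to 63 low-IP infants in 200. Specificity 0.90 then runs from 65-98% (14 infants) to 80-95% (63 infants), and specificity 0.95 from 71-99% to 87-98%. Even at 63 infants the half-widths are 7.6 and 5.8 points. For N=200 to give 0.05, low-IP infants would have to be about 36% of the cohort (72.99/200, specificity 0.95) or 69% (138.29/200, specificity 0.90).

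**Evaluable infants.** Section 7.6.1 says "If these GI signs are present throughout the study window, the La/Rh test will not be administered", while section 4.5.2 provides only that "Subjects who discontinue due to being withdrawn or lost to death will be replaced". Some enrolled infants may therefore have no IP label and not be replaced. The documents give no rate. If 80% were evaluable (assumption), 200 × 0.8 × 0.17 = 27 would be low IP, and specificity 0.90 would have an interval of 73-97%.

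**Secondary wording point.** The sentence refers to change in IP, but under section 2.5 IP is "measured by the urinary La/Rh ratio at one timepoint between d7-10 of life in 200 preterm infants". Section 2.3 reports "intestinal permeability at study time points day 1, 8, and 15 for a cohort of 43 preterm infants", so only the first cohort has repeated measurements.

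**The case against.** The strongest objection is that the sentence never says outright that the 0.05 belongs to specificity. Grammatically it sits with the correlations, and sensitivity and specificity follow as expected values. That is fair, and the sensitivity-only origin is an inference. The alternative readings do not make the sentence correct, however:

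- *Correlations.* By Fisher's z at n=200 the half-width is 0.139 at r=0 and 0.105 at r=0.5. It reaches 0.05 only near r=0.80, and no r is stated.
- *The 83% itself.* 3.8416 × 0.83 × 0.17 / 0.0025 = 217. That lies inside the range but does not produce 166 or 236, and N=200 gives ±5.2 points.
- *One-sided 95%.* Sensitivity 0.80 would then need 209. Specificity would still miss, at 0.057-0.093 across 166-236, and 236 is not reproduced.

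A second objection is that section 10.6 labels samples, and each infant gives several stools, so sample-level specificity may be more precise than 34 infants suggest. Repeated stools add no low-IP infants, because the label comes from one test per infant. The gain depends on a within-infant correlation that the documents do not give. As an illustration (assumption), 10 stools per infant at correlation 0.4 give 340/(1 + 9 × 0.4) = 74 effective observations. That is about enough for specificity 0.95 but not for 0.90, which needs 139. The argument also does not help the stool markers, which are assessed day by day.

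Two points stand. The miss for sensitivity 0.80 is small, about one point at N=200, so the substance is specificity. And simple Wilson intervals assume a cut-off fixed in advance and independent infants, whereas section 10.6 scans many cut-offs and section 4.2 does not exclude twins; the true precision could be somewhat worse than shown.

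**Conclusion.** The concern holds. On the plan's own inputs, 166-236 infants do not give a 0.05 margin for any stated specificity or for sensitivity 0.80. At N=200 the specificity half-width is 0.073 to 0.101, roughly 1.5 to 2 times the figure given. Sensitivity 0.90 does meet the target.

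This rests on the 83% share, two-sided 95% intervals and one IP label per infant. The failure for specificity does not depend on how the printed range was derived, and it persists at the favourable end of the uncertainty in the 83%.

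The damage is limited to the stated precision of the secondary marker and classifier analyses. The primary objective, describing the distribution of La/Rh, is unaffected, and no decision in the plan is tied to the 5 points. It should be corrected because it is the only justification given for the sample size.

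**What to change.** Keep N=200. In section 10.5, delete the claim that 166-236 infants give a 0.05 margin and state the expected precision instead, for example:

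> With 200 evaluable infants and 83% high IP (about 166 high, 34 low), the expected 95% Wilson interval is 84-94% for sensitivity 0.90, 73-85% for sensitivity 0.80, 82-99% for specificity 0.95 and 76-96% for specificity 0.90. Precision for specificity will be lower if fewer infants are low IP or evaluable.

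A clause saying that these intervals assume a pre-fixed cut-off and independent infants would be a useful addition. If a correlation precision is also quoted, give the r it assumes (at n=200, about ±0.14 at r=0 and ±0.10 at r=0.5). Replace the reference to change in IP with IP at 7-10 days.

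The cost is the wording of one paragraph: no extra infants and no change to any analysis. The stated precision becomes less favourable.

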### 10.5 Safety Review *(if applicable)*

## 10.6 Final Analysis Plan

**Primary Objective:** To estimate mean, variance, and quantiles in IP measured by urinary Lacutlose/Rhamnose ratio in in neonates born between 24 and 32 weeks of gestational age.

Sample quantiles of the distribution of IP (as measured by urine LA/Rh ratio) will be calculated at each time point. In addition, we will use mixed effects models to estimate the mean and variance of urine La/Rh. By including other terms in the model we will be able to assess whether high IP (La/Rh ratio  $>0.05$ ) is affected by gestational age, birthweight, sex or *feeding type (mother's own breast milk only, donor breastmilk, preterm formula only, or both breast milk and preterm formula).*

**Secondary Objective:** To evaluate the performance of stool calprotectin, sIgA, and lactoferrin as markers for intestinal permeability *in vivo* as established by the gold standard urine La/Rh in preterm neonates.

**Assessing the relationships between stool markers and urine La/Rh ratio:** To quantify the association between stool calprotectin, sIgA, and lactoferrin, and urine La/Rh ratio, we will calculate Pearson Correlation Coefficients. If the distribution of either variable exhibits substantial skewness we will substitute Spearman Correlation Coefficients. In addition, we will perform sub-group analyses by gestational age or birthweight.

**Assessing the sensitivity and specificity of calprotectin, sIgA, and lactoferrin for identifying children with leaky gut syndrome using an ROC analysis.** Leaky gut syndrome will be defined as having a urinary La/Rh ratio of greater than 0.05 at 7-10 d (12). Using this definition, we will assess the sensitivity, specificity, and predictive value of calprotectin, sIgA, and lactoferrin on each day for identifying those with leaky gut syndrome. An analogous calculation will be made to estimate specificity. We will perform these calculations for a large range of cut-offs for the stool markers, and summarize the findings using an ROC curve. The area under the ROC curve (AUC) will be calculated using an empirical approach to provide an overall summary measure of the performance of **calprotectin, sIgA, and lactoferrin** as measures for leaky gut syndrome.

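### The 0.05 margin given for microbiota–permeability correlations matches a formula for a proportion; near r = 0 the 95% half-width at N = 166–236 is 0.15–0.13

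*Combined protocol and SAP*

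**What the plan says.** The microbiome paragraph of Sample Size Considerations (section 10.5) opens with the reason for the total: "The sample size of 200 was calculated to obtain high precision in correlations between features of the stool microbiota and intestinal permeability (IP"). The next sentence begins from a prevalence, "Since 83% subjects in the first cohort had high IP", and says that 166–236 infants "provides marginal error of 0.05 (maximum sampling error of 5%) and alpha of 0.05 (95% confidence level) to detect correlations" between microbiota features and changes in permeability. It then adds a second aim: "to achieve an expected sensitivity of 0.8-0.9 and expected specificity at 0.9-0.95". The version 2.1 entry in the revision history repeats this, but the section 10 text is current and is the text at issue.

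Section 2.3 relies on the figure. It describes the 200 as a powered cohort and as the reason to "recruit additional 157 preterm subjects and to combine with our existing 43 preterm subjects". The plan gives no expected correlation, no smallest correlation to be detected and no power. The Final Analysis Plan (section 10.6) specifies Pearson coefficients for calprotectin, sIgA and lactoferrin against the La/Rh ratio, with a fallback: "If the distribution of either variable exhibits substantial skewness we will substitute Spearman Correlation Coefficients". For the microbiome data it describes a supervised classifier of high versus low permeability.

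**The concern.** The inputs to the sample size sentence are a prevalence, a sensitivity and a specificity. These fix the precision of a proportion and say nothing about the precision of a correlation coefficient. Yet the sentence attaches the 0.05 to correlations, and the sentence before it gives correlations as the reason for 200.

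The relation of the microbiome to La/Rh is Secondary Objective 1, and this paragraph is the plan's numerical case for 200 infants. A reader who trusts it will treat every reported microbiota–permeability coefficient as accurate to within 0.05. Weak and moderate correlations would then look far better determined than they are.

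**Working it through.** **Inputs from the plan.** N = 166–236 with 200 planned; margin 0.05; 95% confidence, taken as two-sided because sidedness is not stated; prevalence of high permeability 0.83; expected sensitivity 0.8–0.9 and specificity 0.9–0.95 (all Sample Size Considerations). No expected r is given, so r is an assumption and is shown as a range.

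**Step 1: where 166–236 comes from.** The number of infants needed to estimate a sensitivity Se to within 0.05, when only the 83% with high permeability contribute, is

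N = 1.96² × Se(1 − Se) / 0.05² / 0.83

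- Se = 0.90: 138.3 / 0.83 = 166.6 (plan: 166)
- Se = 0.85: 195.9 / 0.83 = 236.04 (plan: 236)
- Se = 0.80: 245.9 / 0.83 = 296.2 (outside the plan's range)

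Other readings do not give the range. A single proportion of 0.83 gives 216.8, and a proportion of 0.5 gives 384.1. Specificity of 0.90 or 0.95 among the 17% with low permeability gives 813.5 or 429.3. A one-sided z gives 117.3, 166.2 and 208.6 for Se = 0.90, 0.85 and 0.80, and so never reaches 236.

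**Step 2: the margin for a correlation.** The Fisher z interval is tanh(atanh(r) ± 1.96/√(N − 3)). Half the width of that interval is:

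| r | N = 166 | N = 200 | N = 236 |
|---|---|---|---|
| 0 | 0.152 | 0.139 | 0.128 |
| 0.3 | 0.139 | 0.126 | 0.116 |
| 0.5 | 0.115 | 0.105 | 0.096 |
| 0.8 | 0.056 | 0.051 | 0.047 |

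The plan calls its 5% a maximum error, so the fair comparison is r = 0, where the half-width is largest. There it is 0.152/0.05 = 3.0, 0.139/0.05 = 2.8 and 0.128/0.05 = 2.6 times the stated figure. A half-width of 0.05 is reached only at |r| of about 0.82, 0.80 and 0.78 for N = 166, 200 and 236. With the Spearman variance (1 + r²/2)/(N − 3), the result is the same at r = 0 and slightly wider above it (0.111 at r = 0.5, N = 200).

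**Step 3: what a true 0.05 margin would take.** The smallest N with a half-width of 0.05 or less is 1,538 at r = 0, 1,274 at r = 0.3, 867 at r = 0.5, 404 at r = 0.7 and 205 at r = 0.8.

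**Step 4: an example.** Take an observed r = 0.15 at N = 200. atanh(0.15) = 0.151 and 1.96/√197 = 0.140, so the 95% interval runs from tanh(0.011) to tanh(0.291), or 0.011 to 0.283. The plan's margin would give 0.10 to 0.20.

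**Step 5: detectable correlation at N = 200, 80% power.** |r| = tanh((z for alpha + 0.842)/√197). This gives 0.197 for one two-sided test at 0.05. With Bonferroni adjustment it gives 0.216 for 2 tests, 0.269 for 20 and 0.299 for 100. These test counts are illustrative; the plan does not give the number of features.

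**The case against.** The best reply is that the 0.05 was meant for sensitivity. The sentence goes on to name sensitivity and specificity. The microbiome analysis in section 10.6 is a classifier, for which those are the natural measures, and Secondary Objective 1 speaks of association; the word correlation appears in Secondary Objective 2. On this reading the plan uses correlation loosely. That is a plausible account of how the sentence arose, and step 1 supports it. It does not rescue the text, which gives precision in correlations as the reason for 200 and ties the margin to them. If sensitivity was meant, the remedy is the same: take the margin off correlations. Whether 0.05 holds for sensitivity and specificity is a separate question.

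Four stronger readings are tempting, and the documents do not support them.

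- That the error is threefold everywhere. It is 2.6 to 3.0 times near r = 0, about twice at r = 0.5, and close to nothing near |r| = 0.8.
- That an estimate such as r = 0.15 would have an interval including zero. At the planned 200 it does not (0.011 to 0.283). It does so only near the bottom of the range (about −0.002 to 0.296 at N = 166).
- That the range follows exactly from stated inputs. The 166 needs 166.6 to be truncated, and the 0.85 is inferred, since the plan gives only 0.8–0.9. The match is close, but the derivation is an inference.
- That the study is too small and should enrol more. The plan sets no target correlation against which 200 could fail, the objective is secondary, and any reported coefficient can carry its own interval.

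**Conclusion.** The precision statement is wrong as written for correlations. With about 200 complete pairs, the 95% half-width is about 0.14 for a correlation near zero and 0.10 for one of 0.5. The stated 0.05 is reached only for correlations near 0.8.

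The correlation figures rest on a two-sided 95% interval, the Fisher approximation, one stool–urine pair per infant and complete data. The last is optimistic: section 10.6 uses available data, and section 7.6.1 allows the La/Rh test to be withheld. If only 157 pairs were available (an illustrative number), the half-width at r = 0 would be 0.157. The conclusion does not depend on how 166–236 was derived, because the half-widths follow from N alone.

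**What to change.** In the microbiome paragraph of Sample Size Considerations, detach the 0.05 margin and the high-precision claim from correlations. Add wording such as:

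> With 200 complete stool–urine pairs, the 95% half-width for a correlation is about 0.14 near r = 0, 0.13 at r = 0.3 and 0.10 at r = 0.5. At two-sided alpha 0.05, 80% power requires |r| of at least about 0.20 for a single test, and more if several features are tested (for illustration, 0.22 for 2, 0.27 for 20 and 0.30 for 100 with Bonferroni adjustment). Missing pairs widen these figures.

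If the 0.05 is kept for sensitivity, say so and give the assumed sensitivity values. The cost is a change of wording and a less favourable stated precision. Enrolment, procedures and analyses are unaffected. Naming particular taxa as the main correlations is optional and not part of this correction.

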**Endpoints:**

Onetime measurement of *in vivo* permeability determined by the urine La/Rh ratio between 7-10 days of age and serial stool microbiome changes between postnatal d5-d14 and at PND21 in a cohort of preterm neonates. The goal is to determine the changes in the intestinal microbiome characteristics in association with impaired intestinal barrier function (La/Rh  $\geq 0.05$ ) at 7-10 days in preterm neonates.

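### The N=200 sample-size text promises correlations with change in intestinal permeability, but within-infant change can be computed in at most 43 of the 200 infants

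*Combined protocol and SAP*

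**What the plan says.** Section 10.5, in the paragraph on the microbiome analysis, opens by tying precision at 200 infants to correlations of stool microbiota features with intestinal permeability (IP), without mentioning change. The next sentence says that the sample size serves "to detect correlations between features of the microbiota and changes in IP".

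Section 2.3 plans to "recruit additional 157 preterm subjects and to combine with our existing 43 preterm subjects" and calls the result a statistically powered cohort. Its hypothesis is that two bacterial groups "are rapidly gaining prosperity during normal intestine development in association with improved barrier function measured by La/Rh ratio".

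The measurement schedule is narrower. The endpoint in the Protocol Summary is "Onetime measurement of *in vivo* permeability determined by the urine La/Rh ratio between 7-10 days of age", together with serial stool microbiome changes. Section 2.5 measures La/Rh "at one timepoint between d7-10 of life in 200 preterm infants 24-32 weeks gestation". Sections 6.4 and 6.9 and Appendix A agree: one dose and one urine collection at that visit. The revision history dates the cut to a single test to version 2.0 (2018). It lists the increase to 200, with the same wording about change, under version 2.1 (2019). The change wording therefore came in after serial testing had been dropped.

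Two pieces of analysis text still read as if IP were measured repeatedly. The primary-objective paragraph of 10.5, still written for 50 subjects, and the primary analysis in 10.6 both refer to each time point. Section 10.6 also plans mixed effects models without naming a grouping factor.

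**The concern.** A reader of 10.5 and 2.3 would expect the 200-infant dataset to relate the microbiota to how IP moves within an infant. For the new infants, no such movement is recorded.

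The distinction matters on the plan's own evidence. Section 10.5 reports that 83% of the first cohort had high IP at study day 8. Section 2.3 describes maturation over the first two weeks and adds that "in some infants, high IP persisted and/or recurred in association with altered levels of the normal microbiota". One high value at 7-10 days cannot separate an infant whose barrier is still maturing from one in whom high IP has persisted or recurred.

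At stake is what the 200-infant result may be said to show. A cross-sectional association at 7-10 days could be described as an association with improvement. It could then be carried in that form into the detection method proposed in 2.3 and the future probiotic study mentioned in 2.5.

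**Working it through.** **1. The plan's own figure.** Section 10.5 gives a range of 166-236, with margin d = 0.05, 95% confidence, prevalence of high IP 0.83, sensitivity 0.8-0.9 and specificity 0.9-0.95. The standard formula for the precision of a sensitivity is N = 1.96² × Se(1 − Se) / d² / prevalence.

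- Se 0.90: 138.3 / 0.83 = 166.6, which matches 166.
- Se 0.85: 195.9 / 0.83 = 236.0, which matches 236.
- Se 0.80: 245.9 / 0.83 = 296.2, which does not match.

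The range therefore corresponds to sensitivity 0.85-0.90, not to the stated 0.8-0.9. That mismatch is a separate matter. What counts here is that the figures that match come from the precision of a proportion. No input is a correlation or a change in IP. A half-width of 0.05 for a correlation near zero would need (1.96 / atanh 0.05)² + 3, or about 1,537 infants.

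**2. Who has more than one IP value.**

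- New infants: 200 − 43 = 157, or 78.5%. Each has one scheduled test. The repeat in 6.9 applies only when less than 2 ml of urine was collected, and it falls inside the same 7-10 day window. It replaces a failed test and adds no time point.
- First cohort: 43 of 200, or 21.5%. The Figure 1 legend in 2.3 gives IP at study days 1, 8 and 15.
- Section 6.7 asks for a La/Rh test at early termination if possible. That could give an occasional second value, but it is not a scheduled measure of change.

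**3. Precision of a correlation.** On the Fisher z scale the 95% half-width is 1.96/√(n − 3), taken back to r by tanh, for r near 0. The smallest r detectable with 80% power at two-sided 0.05 is tanh[(1.960 + 0.842)/√(n − 3)].

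| Quantity | n | 95% half-width | Detectable r |
|---|---|---|---|
| Change in IP, first cohort only | 43 | tanh(1.96/√40) = 0.30 | 0.42 |
| Level of IP at 7-10 days | 200 | tanh(1.96/√197) = 0.14 | 0.20 |

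The first row assumes complete serial data in all 43. The second assumes a usable La/Rh value in all 200, and counts the first cohort's study-day-8 test as a 7-10 day value; the revision history equates the two approximately.

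**4. What the formal aims ask.** The primary objective (2.5) is the mean, variance and quantiles of IP at 7-10 days. The first secondary objective is the association of the microbiome with IP. The outcome measures (3.2) are quantitative IP and a binary leaky-gut indicator. The ROC analysis and the classifier (10.6) use La/Rh above 0.05. All of these need one value per infant.

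**The case against.** The strongest reply is that this is loose wording around a sound design. Much of that reply stands.

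- No formal objective or endpoint asks for change in IP. The changes named in the endpoint are in the microbiome, which is sampled serially. A reader might infer that the study's stated aims cannot be answered at N=200; the documents do not support that.
- The phrase that describes the bacteria "as a strong indicator to the lowered IP and rapid maturation of intestinal barrier" reports previous findings. It is not an aim for the 200.
- The single test is a reasoned choice. The revision history says that infants with normal and delayed barrier maturation already differed significantly at the second time point, about 7-10 days of age. Improved barrier function can then be read as lower La/Rh between infants at that age.
- No change score is planned in 10.6, so misreporting as maturation is a risk, not a planned step.
- A reader might also argue that a low value at 7-10 days could come from an infant whose IP was never high. Section 2.3 does not say so; it says that IP is high at birth in preterm infants. Only the ambiguity of a high value, between delayed maturation, persistence and recurrence, has support.
- Mixed models need not imply repeated measures. Twins are eligible under 4.2, and a sibling-pair effect would be legitimate with one value per infant. Section 10.6 does not say that this is the purpose.

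None of this makes a level into a change. The evidence for using the level as a proxy comes from the first cohort, and nothing in 10.6 tests one value as a measure of trajectory. The sample-size sentence also goes beyond the opening sentence of its own paragraph and beyond the protocol's objectives.

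**Conclusion.** The point holds as a mismatch between the stated purpose of N=200 and the schedule. Within-infant change in IP is available for at most 43 of 200 infants and for none of the 157 new ones under the scheduled visits. The high precision claimed for 200 belongs to the level of IP at 7-10 days. For change, the half-width is about twice as large (0.30 against 0.14), under the completeness assumptions given above. The change question is thus answerable only imprecisely, and only in the first cohort. The formal objectives, the endpoint, the marker analyses and the classifier are unaffected. The text should be corrected, because it credits the full cohort with a property that the single-test design does not have.

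**What to change.** 1. In the microbiome paragraph of 10.5, replace the reference to changes in IP with the La/Rh ratio at postnatal days 7-10.
2. In 2.3, state the hypothesis for the 200 infants as a between-infant association with the La/Rh level at that age.
3. In 10.5 and 10.6, restrict the each-time-point wording and any repeated-measures use of mixed effects models to the 43 infants with serial tests. For the 200, specify a single-time-point analysis at 7-10 days. If a mixed model is kept there for twin pairs, name that grouping factor.
4. Report any result on within-infant maturation, improvement, persistence or recurrence of IP for the first cohort only, with the number of infants who have the serial values.

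This needs no extra test, infant or visit. The cost is a narrower stated claim for the 200-infant cohort.
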